### **7.4 Unscheduled Visit**

Subjects will be permitted to return for unscheduled visits between scheduled visits as needed to address issues related to AEs, continuing or new symptoms, or other problems as they arise. Any of the following activities may be performed at the discretion of the site PI (note that some items are only relevant to a subset of subjects):

- Medical history will be reviewed (including review of interval medical records and local laboratory results, if available) and updated as appropriate. If the local laboratory results indicate a need for retreatment for syphilis infection, the subject will receive treatment according to the local clinic's standard protocols and will be withdrawn from the study per protocol Section 5.3.3.
- Interim sexual history since the last study visit will be collected. Specimens will be collected at sites of exposure for STI screening/diagnosis as indicated by local standard of care and subject history.

- A urine pregnancy test will be performed on all subjects of childbearing potential.
- All concomitant medications taken since the last study visit will be recorded on the appropriate data collection form. Previously recorded medications will be updated as appropriate.
- Study personnel will discuss with subjects and assess and record all AEs/SAEs. Previously recorded AEs/SAEs will be updated as appropriate.
- A targeted physical examination will be performed by a qualified study clinician (including vital signs: temperature, heart rate, respiration rate, and blood pressure; and genital, rectal, oral, skin, and lymph node examinations).
- Contact information will be reviewed.

## **8 STUDY PROCEDURES/EVALUATIONS**

### **8.1 Clinical Evaluations**

Complete medical history will be obtained by interviewing the subjects at Visit 1 (and reviewing medical records for the past 14 days, if available) and will be updated at each clinic visit. At follow-up visits, an interim medical history will be obtained by interviewing the subjects (and reviewing interval medical records, if available), noting any changes since the previous visit.

Sexual history for the past 60 days will be obtained by interviewing the subjects at Visit 1. At follow-up visits, an interim sexual history will be obtained by interviewing the subjects, noting any changes since the previous visit.

Medications history (concomitant medications) will include a review of all current medications and medications taken 30 days before initiating study treatment. Prescription and over-the-counter drugs will be included as well as vitamins, herbs, and supplements. Assessment of eligibility will also include a review of all permitted and prohibited medications per the Subject Inclusion and Exclusion Criteria (see Section 5).

A targeted physical examination (vital signs (temperature, heart rate, respiration rate, and blood pressure); genital, rectal, oral, skin, and lymph node examinations) will be performed at each visit. All physical examinations will be performed by a qualified study clinician.

#### **Evaluation for symptoms of a Jarisch-Herxheimer reaction**

Approximately 24 hours after Visit 1, the subjects will be contacted as noted in Section 7.1 and evaluated for symptoms of a Jarisch-Herxheimer reaction. During this assessment, subjects should refer to the completed Jarisch-Herxheimer checklist distributed at Visit 1. Subjects will be asked about fever (confirmed by thermometer at home close to the time of fever onset, if possible), chills, myalgia, weakness, flushing, worsening of skin rash, tachycardia (i.e., fast heartbeat), heart palpitations, arthralgia, nausea, headache, and dizziness, including time of onset and time of resolution of each symptom reported. If subjects cannot be reached after Visit 1, the evaluation for symptoms of a Jarisch-Herxheimer reaction will be conducted at Visit 2 (per Section 7.1, all subjects will be asked to bring the completed checklist with them to Visit 2). Data will be recorded on the appropriate eCRF(s) based on subject interview during the non-visit contact or at Visit 2 if the contact is not successful; the Jarisch-Herxheimer checklist completed by the subject will not be retained.

#### **Evaluation for resolution of clinical signs of syphilis infection**

At Visit 2 and Visit 3, subjects will be evaluated for resolution of signs of syphilis documented at Visit 1, as noted in Section 7.

## **8.2 Laboratory Evaluations**

### **8.2.1 Clinical Laboratory Evaluations**

Diagnostic laboratory tests for HIV and other STIs as indicated will be performed locally according to local protocols. Phlebotomy for serological testing and serum storage to determine study outcomes will be performed locally with testing carried out at the Central Laboratory. Serological testing may also be conducted locally according to local protocols.

A pregnancy test will be performed at all visits on all subjects of childbearing potential; a urine or serum pregnancy test is permitted at Visit 1, while a urine pregnancy test is to be performed at all other visits. Results must be negative and known prior to randomization at Visit 1.

### **8.2.2 Special Assays or Procedures**

At Visit 1, study staff will swab consenting subjects' oral cavities and primary or secondary lesions (if lesions are present per Section 5.1). Swabs will be stored in study-specific medium and shipped to the [name] laboratory at the University of Washington for whole-genome sequencing of *T. pallidum* isolates. Collecting oral swabs and swabs of lesions (if present) is optional, and additional details can be found in the protocol-specific swab guidance manual.

### **8.2.3 Specimen Preparation, Handling, and Shipping**

#### **8.2.3.1 Instructions for Specimen Preparation, Handling, and Storage**

Specimen preparation, handling, and storage will be done according to local clinic SOPs. Additional details can be found in the protocol-specific MOP.

#### **8.2.3.2 Specimen Shipment**

Specimen shipment to the Central Laboratory will occur according to all applicable International Air Transport Association (IATA) requirements. Additional details can be found in the protocol-specific MOP.

## **9 ASSESSMENT OF SAFETY**

### **9.1 Specification of Safety Parameters**

Safety will be monitored throughout the study by physical examination (including vital signs: temperature, heart rate, respiration rate, and blood pressure; and genital, rectal, oral, skin, and lymph node examinations) and subject reporting. Safety will be assessed by the frequency and severity of AEs/SAEs (including solicited reactogenicity AEs and other unsolicited AEs) occurring from the time of study product administration through the Month 1 visit.

### **9.2 Methods and Timing for Assessing, Recording, and Analyzing Safety Parameters**

#### **9.2.1 Adverse Events**

##### **Adverse Event:**

ICH E6 GCP defines an AE as any untoward medical occurrence in a clinical research subject administered a study drug regardless of its causal relationship to the study drug. An AE can therefore be any unfavorable and unintended sign (including an abnormal laboratory finding), symptom, or disease temporally associated with the use of the study drug. The occurrence of an AE may come to the attention of study personnel during study visits and interviews of a study subject presenting for medical care or upon review by a study monitor. Since the safety profile of BPG (both 1 and 3 doses) is well established, and this study is not powered to detect new, unknown safety signals, non-serious AEs will not be reported to the DSMB.

All AEs not meeting the criteria for SAEs should be captured on the appropriate eCRF. Information to be collected includes event description, time of onset, clinician's assessment of severity, relationship to study drug (assessed only by those with the training and authority to make a diagnosis), and time of resolution/stabilization of the event. All AEs occurring while on study must be documented appropriately regardless of relationship. All AEs will be followed to adequate resolution.

Any medical condition that is present at the time that the subject is screened should be considered as a baseline finding and not reported as an AE. However, if it deteriorates at any time during the study, it should be recorded as an AE.

All AEs must be graded for severity and relationship to the study drug.

The US Food and Drug Administration (FDA) defines an AE as any untoward medical occurrence associated with the use of a drug in humans, whether or not considered drug-related.

**Severity of Event:** All AEs will be assessed by the clinician using a protocol-defined grading system (see Appendix B).

Changes in the severity of an AE should be documented to allow an assessment of its duration at each level of intensity to be performed. AEs characterized as intermittent require documentation of onset and duration of each episode.

**Relationship to Study Drug:** The clinician's assessment of an AE's relationship to the study drug is part of the documentation process, but it is not a factor in determining what is or is not reported in the study. If there is any doubt as to whether a clinical observation is an AE, it should be reported. All AEs must have their relationship to the study drug assessed using the terms "related" or "not related," as defined below. In a clinical trial, the study drug must always be suspect.

- **Related** – There is a reasonable possibility that the study drug caused the AE. Reasonable possibility means that there is evidence to suggest a causal relationship between the study drug and the AE.
- **Not Related** – There is not a reasonable possibility that administration of the study drug caused the AE.

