### 9.2.2 Reactogenicity

Reactogenicity events are AEs that are common and known to occur for the study drug being studied. For this protocol, the following reactogenicity events are expected to occur among some subjects:

- Systemic reactions: Jarisch-Herxheimer reaction (as described in protocol Section 8.1)
- Local injection site reactions: pain or tenderness, erythema or redness, induration or swelling

Reactogenicity events (as solicited AEs), along with unsolicited AEs, will be assessed at the visits specified in protocol Section 7 and will be graded using a protocol-defined grading system (see Appendix B).

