## **9.5 Halting Rules**

Further enrollment will be halted for DSMB review if any of the following are reported:

- If one or more subjects experience an SAE judged by an investigator to be related to the study drug
- An overall pattern of clinical events that the DMID Medical Monitor or DSMB consider associated with the study drug and that may appear minor in terms of individual events, but that may collectively represent a serious potential concern for safety

If any of the halting rules are met, the study will not continue with the remaining enrollments or study treatments without a review by and recommendation from the DSMB to proceed.

DMID retains the authority to suspend additional enrollment and administration of the study drug during the entire study, as applicable.

---

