## 9.6 Safety Oversight (ISM plus DSMB)

An ISM at each clinical research site will oversee the safety of research subjects at that site and will provide independent written evaluation of SAEs and related Grade 3 AEs to the PI, DMID Clinical Project Manager, and DMID Medical Monitor. The ISM will serve as an independent consultant for the site PI on subject-related issues. The ISM will communicate with the site PI and study PIs to resolve any issues.

Safety oversight will be conducted by a DSMB that is an independent group of experts that monitors subject safety and advises DMID. The DSMB members will be separate and independent of study personnel participating in this trial and should not have scientific, financial, or other conflict of interest related to the study. The DSMB will consist of members with appropriate expertise to contribute to the interpretation of the data from this trial.

The DSMB will review safety and enrollment data when half of the study subjects have been enrolled and observed for SAEs through the Month 1 Visit.

The DSMB will review study progress and subject clinical and safety data at the following time points:

- At least annually after the first subject is enrolled.
- Ad hoc when a halting rule is met, for immediate concerns regarding observations during the study, or as needed.
- During a final closeout meeting, held at the end of the study after the database is locked to review cumulative study data prior to finalizing the Clinical Study Report (CSR).

The DSMB will operate under the rules of a DMID-approved charter that will be written at the organizational meeting of the DSMB. As an outcome of each review/meeting, the DSMB will make a recommendation as to the advisability of proceeding with study administrations (as applicable), and to continue, modify, or terminate the study.

DMID or the DSMB chair may convene the DSMB on an ad hoc basis according to protocol criteria or if there are immediate concerns regarding observations during the study. The DMID Medical Monitor is empowered to stop enrollment and study treatment if SAEs that meet the halting criteria are reported. The DMID Medical Monitor will be responsible for reviewing SAEs in real time. The DSMB will review SAEs on a regular basis and *ad hoc* during the study.

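### The protocol withholds non-serious adverse events from the DSMB, yet names the DSMB as a judge of a halting rule built on individually minor events

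*Protocol*

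**What the plan says.** Four parts of the protocol bear on what the DSMB sees.

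- **Section 9.2.1** gives the reporting rule: "non-serious AEs will not be reported to the DSMB". The reasons offered are that the safety of both schedules is already well known and that "this study is not powered to detect new, unknown safety signals". No exception is stated.
- **Section 9.5** has two halting rules. The first is met by a single SAE that an investigator judges related. The second is met by "An overall pattern of clinical events that the DMID Medical Monitor or DSMB consider associated with the study drug", qualified as one "that may appear minor in terms of individual events, but that may collectively represent a serious potential concern for safety". Once either is met, enrollment and treatment may not resume "without a review by and recommendation from the DSMB to proceed".
- **Section 9.6** says "The DSMB will review study progress and subject clinical and safety data at the following time points" and lists those times: at least yearly, ad hoc, and at close-out after database lock. It also sets a review at half enrollment, timed on observation for SAEs through Month 1. The Medical Monitor reviews SAEs in real time. Each site's ISM sends written evaluations of SAEs and related Grade 3 AEs to the PI, the Clinical Project Manager and the Medical Monitor. The DSMB is not among those recipients.
- **Section 15.4** allows safety summaries to be produced for the DSMB but does not require them or define their content.

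Section 9.2.2 adds that "Reactogenicity events are AEs that are common and known to occur for the study drug being studied". Non-serious injection-site and Jarisch-Herxheimer reactions therefore fall under the same reporting rule.

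**The concern.** A halting rule is only as good as the data that reach whoever must apply it. Section 9.5 gives the DSMB two roles under the pattern rule: it may identify the pattern itself, and it must review any pattern raised by someone else before the trial goes on. The events in question are ones that look minor singly, and most such events will be non-serious AEs. Section 9.2.1 removes those from what the board receives.

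At stake is the board's ability to notice, while enrollment is open, that non-serious reactions are accumulating or differ between arms. Such a difference is plausible by design. Under Section 6.2 each dose is two injections, so Arm 1 receives 1 × 2 = 2 injections and Arm 2 receives 3 × 2 = 6, and Section 2.3.1 already expects more local discomfort in the arm with extra doses. Whether any such excess would amount to a serious concern is for the board to judge, but it cannot judge what it is not shown.

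**Working it through.** No figure in the protocol is in dispute and no calculation applies. The check is to follow each class of event to the people who can act under Section 9.5.

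| Event class | Stated route to Medical Monitor | Stated route to DSMB |
|---|---|---|
| SAE, related | Yes (9.3.1, 9.6) | Yes; also halts enrollment by itself (9.2.3, 9.5) |
| SAE, not related | Yes (9.3.1, 9.6) | Yes, periodic review (9.2.3, 9.6) |
| Non-serious, Grade 3, related | Yes, through site ISMs (9.6) | No (9.2.1) |
| Non-serious, Grade 3, not related | None stated | No (9.2.1) |
| Non-serious, Grade 1–2 | None stated | No (9.2.1) |

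1. **The DSMB identifying a pattern.** It receives the first two rows. The first already halts enrollment under the other rule. What remains for the pattern rule is a cluster of SAEs that investigators judged unrelated. That is a real use of the rule, but it is not the kind of event the wording about minor events chiefly describes.

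2. **The DSMB reviewing a pattern raised by the Medical Monitor.** Section 9.5 makes this review compulsory, and Section 9.6 provides for an ad hoc meeting. Section 9.2.1 makes no exception for that meeting, so on a literal reading the board would be asked to rule on events it is not to receive.

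3. **The Medical Monitor identifying a pattern.** This role receives the first three rows. The last two rows are captured on the eCRF, but no routine central review of them during the trial is described.

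4. **Whether other text repairs the gap.** The general phrase in Section 9.6 about clinical and safety data either includes non-serious AEs, and then conflicts with Section 9.2.1, or excludes them, and then leaves the gap. The summaries in Section 15.4 are optional. The close-out review covers cumulative data but follows database lock, too late for a rule about halting enrollment. The by-treatment AE tabulations in Section 11.4.3 belong to the final analysis.

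On any reading, Sections 9.2.1, 9.5, 9.6 and 15.4 do not together say which AE data the DSMB holds when it applies or reviews the pattern rule.

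**The case against.** A good case can be made for the sponsor. The pattern rule is disjunctive: the Medical Monitor alone can trigger it, and DSMB review then follows. Related Grade 3 events from every site reach that one central person. Seriousness and severity are separate scales, so a cluster of SAEs judged unrelated could meet the rule, and the board does see those. This is a Phase 4 trial of a marketed drug outside an IND, one related SAE halts enrollment, and Section 9.2.1 gives reasons for limiting the reporting. Section 11.3.1 also refers to a DSMB charter, which is not among the documents and may define the board's reports more fully.

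Much of this stands, and it rules out two stronger readings. A reader might infer that the pattern rule is inoperative. It is not, because the Medical Monitor can invoke it in part and the DSMB keeps a narrow use of it. A reader might also infer that severe non-serious reactions would escape all central oversight. Section 9.6 contradicts that for Grade 3 events judged related: they reach the Medical Monitor, though not the board.

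The conflict itself remains. The stated reasons support not sending individual reports; they do not explain naming the DSMB as judge of a pattern of minor events and then withholding those events. Limited power for new signals is no reason to keep descriptive counts from the board. A charter could supply the data, but it would then contradict the unqualified sentence in Section 9.2.1.

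**Conclusion.** The contradiction between Section 9.2.1 and Section 9.5 is real and can be read from the text alone. The DSMB is given a role in a halting rule without most of the data that rule concerns, and the Medical Monitor's stated information covers only part of the gap. The uncovered part is Grade 1–2 events and non-serious Grade 3 events judged unrelated, for which no central route during the trial is stated.

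The size is moderate. The rule is weakened rather than disabled, the related-SAE halt works as written, and the primary analysis, error rate and power are untouched. It should be corrected because the fix is cheap and the rule is one the protocol itself assigns to the board.

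The conclusion assumes that events appearing minor individually are mostly non-serious AEs, which follows from the ordinary sense of Section 9.5 though the protocol does not say so, and that no unseen document overrides Section 9.2.1.

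**What to change.** Reconcile Sections 9.2.1, 9.5, 9.6 and 15.4 on which AE data the DSMB and the Medical Monitor receive, and when. One way that keeps the sponsor's aim of limiting reports is to restate the sentence in Section 9.2.1 along these lines:

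*Non-serious AEs are not reported to the DSMB individually. Each scheduled DSMB report, and the material for any ad hoc review under the pattern halting rule, includes aggregate tables by treatment arm of solicited and unsolicited AEs by severity and relatedness.*

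Section 15.4 should then make these summaries a requirement, Section 9.6 should refer to them, and the DSMB charter should be aligned. Neither the halting criteria nor any clinical procedure needs to change for this.

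The cost is a few extra tables per DSMB report. The data are already required on the eCRF under Section 9.2.1. Because subjects and providers are unmasked (Section 5.3.2), tables by arm for the board break no mask at the sites; they should still go only to the board.

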### 9.2.2 Reactogenicity

Reactogenicity events are AEs that are common and known to occur for the study drug being studied. For this protocol, the following reactogenicity events are expected to occur among some subjects:

- Systemic reactions: Jarisch-Herxheimer reaction (as described in protocol Section 8.1)
- Local injection site reactions: pain or tenderness, erythema or redness, induration or swelling

Reactogenicity events (as solicited AEs), along with unsolicited AEs, will be assessed at the visits specified in protocol Section 7 and will be graded using a protocol-defined grading system (see Appendix B).

